	
To evaluate the impact of laparoscopic surgery on adhesion- related formation, we are planning to perform an update of the SCAR studies to recent years in which a large number of laparoscopic surgeries have been performed. Comparison of readmissions for adhesion- related complications after open and laparoscopic surgery will be made. The study will provide an estimate of the current burden of adhesion-related morbidity in Scotland, which could also serve as a model for the current burden in other European countries. Further such estimate can be used to model the impact of further implementation of anti-adhesion barriers on adhesion-related morbidity and healthcare costs in both Scotland and abroad.

3.1.08	
Provide a full, clear and concise outline of the proposal design, listing: data sources; sample size ; inclusion/exclusion criteria (eg involvement in trial/survey; health event, etc); relevant date range; need for identifiable or potentially identifiable data; requirement for a matched control cohort etc.
 
We intend to use the Scottish National Health Service record linkage capabilities. Inclusion criteria are all patients undergoing initial abdominal or pelvic surgery between June 2009 and June 2011. Selection will be made by OPCS-4 codes related to the admission. A list of relevant codes can be found in the appendix. We choose for these years to allow inclusion of an incident population in a time that laparoscopic surgery had already been implemented and that allows for 4 to 5-years of follow-up.
 
We will exclude patient who had had abdominal or pelvic operation in the 5 years before 2009, as pre-existing adhesions from this prior surgery might influence results. There are no further exclusion criteria.
 
For analyses patients will be grossly divided in three groups of anatomical location of the surgery: hindgut, female reproductive tract, and foregut or other. Within each group subgroups of laparoscopic and open procedures will be made.
 
We expect approximately 70,000- 100,000 patients to have had abdominal or pelvic surgery in the period June 2009- June 2011. Approximately 25,000 are expected to have had prior abdominal surgery in the previous 5 years. Thus, we expect an incident population of 45,000 to 75,000 to be included in the study.

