	
For the study we will analyse re-admission in the years following surgery that are directly related to adhesions, possibly related to adhesions, and readmission with surgery that might be complicated by adhesions. For this purpose we will need a patient identifier that allows to link readmissions to the initial surgery. The data can be anonymized so that the identifier represent just a random number. As baseline characteristics we will only require age and sex. No further potentially identifiable data such as birth date, postal code or NHS number is required.
 
From the initial admission with abdominal or pelvic surgery we need ICD- 10 codes and OPCS- 4 codes describing the type of surgery performed as well as information whether the operation was performed laparoscopic ally or open. This same set of information is needed for any readmission in follow-up. Further we need the time interval (in months) between the index operation and the readmission. Only readmissions coded by one or more relevant ICD-10 or OPCS-4 code need to be included.
 
For a readmission to be classified as directly related to adhesions, an explicit adhesion reference was required in the operative OPCS-4 or diagnostic ICD-10 coding. Adhesions might however not always be coded, especially not if readmission goes without surgery. For example, a conservative treated small bowel obstruction might only be coded as abdominal pain, nausea, and vomiting. Therefore we will define a broader set of operative codes and diagnostic codes that might indicate a possibly adhesion- related complication.
 
Data from follow-up is requested to the latest date from which a complete record can be extracted.

3.1.09	Does the proposal have implications for, or target, sensitive groups or vulnerable populations? Please give details
	No
3.1.10	Does the proposal seek to use information exclusively about deceased persons? Please give details
	No

3.1.11	Have any members of the public/lay representatives been involved in the proposal design? Please give details
	No
3.1.12	Has any peer review of the proposal been undertaken? Please give details (for example formal review by a peer organisation or funding body, informal internal review, review by a third party)
	Informal internal review has been performed within the Radboud University Medical Center, department of Surgery. The research proposal and internal funding for performing the study were approved.

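### The plan does not say how a possibly adhesion-related readmission is classed when the same record codes another cause, so the burden estimate can include disease-driven readmissions

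*Combined protocol and SAP*

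**What the plan says.** Section 3.1.08 names three kinds of readmission: "directly related to adhesions, possibly related to adhesions, and readmission with surgery that might be complicated by adhesions". For the first, "an explicit adhesion reference was required in the operative OPCS-4 or diagnostic ICD-10 coding". For the second, the plan argues that adhesions are often left uncoded, for example that "a conservative treated small bowel obstruction might only be coded as abdominal pain, nausea, and vomiting". It continues: "Therefore we will define a broader set of operative codes and diagnostic codes that might indicate a possibly adhesion- related complication". Nothing is added about the position or number of codes, or about another diagnosis on the same record.

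The paragraph before this, which lists the data requested, ends: "Only readmissions coded by one or more relevant ICD-10 or OPCS-4 code need to be included".

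Other parts of the design that could limit the effect of underlying disease do not mention it. After the exclusion for prior surgery, Section 3.1.08 states: "There are no further exclusion criteria". It also states: "As baseline characteristics we will only require age and sex". The open and laparoscopic subgroups are formed within three anatomical groups, with no division by indication or malignancy. ICD-10 and OPCS-4 codes are requested for the index admission and for every readmission in the extract (Sections 3.1.08 and 4.3).

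On the use of the results, Section 3.1.07 says: "The study will provide an estimate of the current burden of adhesion-related morbidity in Scotland". It adds that the estimate could serve as a model for other European countries and could support modelling of anti-adhesion barriers.

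**The concern.** A class defined by symptoms and other non-specific codes will pick up readmissions that have nothing to do with adhesions. Some of these can be recognised from the record itself. A patient who had a bowel cancer resection in 2010 may return in 2012 with vomiting and obstruction, with recurrent malignancy coded on the same record. The supplied text gives no rule that would exclude this readmission, downgrade it or report it separately, so it can be counted as possibly adhesion-related. An obstructed hernia or a flare of inflammatory bowel disease raises the same question.

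Two results are exposed. The first is the national burden: readmissions caused by the underlying disease would be added to it. Any later barrier model built on that figure would credit barriers with preventing events they cannot prevent. The second is the route comparison, but only conditionally. If patients operated on openly have more underlying disease than laparoscopic patients within the same anatomical group, the extra readmissions would look like an effect of route.

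**Working it through.** **1. The plan's own figure.** The only derived number in the documents is the expected incident population: 70,000 − 25,000 = 45,000 and 100,000 − 25,000 = 75,000. Both match Section 3.1.08. The plan gives no event rate for the new cohort, no effect size and no power, so the size of this problem can only be illustrated.

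**2. Formula.** Cancer serves as the example of underlying disease. For each route:

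observed risk = 1 − (1 − t)(1 − c × r)

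- t: true risk of an adhesion-related readmission, set equal in both routes. Assumed 10%, 20% or 30%.
- c: share of patients in that route with cancer. Assumed 20% in both; 30% open and 10% laparoscopic; or 40% open and 10% laparoscopic.
- r: chance that a cancer patient has a readmission caused by the cancer that carries a listed code. Assumed 5%, 15% or 30%.

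None of these values is in the documents. The formula treats the two kinds of readmission as independent.

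**3. Worked case.** t = 20%, r = 15%, cancer shares 30% open and 10% laparoscopic:

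- open: 1 − 0.80 × (1 − 0.30 × 0.15) = 1 − 0.80 × 0.955 = 23.6%
- laparoscopic: 1 − 0.80 × (1 − 0.10 × 0.15) = 1 − 0.80 × 0.985 = 21.2%
- difference 2.4 points, ratio 23.6 / 21.2 = 1.11, where the truth is 20% in both.

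**4. Results at t = 20%.**

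| Cancer share, open / laparoscopic | r | Open | Laparoscopic | Ratio |
|---|---|---|---|---|
| 20% / 20% | 5% | 20.8% | 20.8% | 1.00 |
| 20% / 20% | 15% | 22.4% | 22.4% | 1.00 |
| 20% / 20% | 30% | 24.8% | 24.8% | 1.00 |
| 30% / 10% | 5% | 21.2% | 20.4% | 1.04 |
| 30% / 10% | 15% | 23.6% | 21.2% | 1.11 |
| 30% / 10% | 30% | 27.2% | 22.4% | 1.21 |
| 40% / 10% | 5% | 21.6% | 20.4% | 1.06 |
| 40% / 10% | 15% | 24.8% | 21.2% | 1.17 |
| 40% / 10% | 30% | 29.6% | 22.4% | 1.32 |

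Over all three values of t:

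- equal shares: burden 0.7 to 5.4 points too high, ratio 1.00 throughout;
- 30% and 10%: spurious difference 0.7 to 5.4 points;
- 40% and 10%: spurious difference 1.05 to 8.1 points;
- spurious ratio across the two unequal settings: 1.02 to 1.64.

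**5. Sample size gives no protection.** Take the case in step 3 and assume one third of patients in each anatomical group and 30% of them laparoscopic. At N = 45,000 one group has 15,000 patients, 4,500 of them laparoscopic. The chance that the purely spurious difference reaches two-sided p < 0.05 within that group is about 90%. At N = 75,000 it is about 99%.

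**6. What simply dropping co-coded readmissions would do.** Keep t = 20% and shares of 30% and 10%. Assume that every disease-driven readmission is removed, but that half of the true adhesive readmissions in cancer patients also carry a malignancy code and are lost:

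- open: 20% − 0.30 × 20% × 0.5 = 20% − 3.0% = 17.0%
- laparoscopic: 20% − 0.10 × 20% × 0.5 = 20% − 1.0% = 19.0%
- ratio 17.0 / 19.0 = 0.89.

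The error now runs the other way and is about as large as the one in step 3.

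**The case against.** A reader might infer from "Only readmissions coded by one or more relevant ICD-10 or OPCS-4 code need to be included" that a single listed code makes a readmission possibly adhesion-related whatever else is coded. The documents do not support that. The sentence says which readmissions enter the extract, and Section 3.4.02 repeats the same limit as data minimisation. Classification is taken up only in the next paragraph of Section 3.1.08. What can be said is that the supplied text leaves the handling of a co-coded cause unstated.

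A reader might also infer that the route comparison is biased. The documents give no disease shares by route. With equal shares the ratio under no true difference stays 1.00, so this is a risk and not a finding.

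Section 3.1.08 is an outline in a data-access application. Section 7 lists a code appendix and the protocol sent for ethics review, neither of which is in the supplied text. A rule could sit there. This stands as a limit on the point. A list of qualifying codes alone would still not settle what happens when a qualifying code and a competing one appear on the same record.

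Three further limits stand:

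- The directly related class needs an explicit adhesion reference and is much less exposed.
- The third class, surgery that adhesions might complicate, does not claim that adhesions caused the readmission. A planned staged operation counted there is not misclassified.
- No headline composite is designated for the new cohort. The 34.6% in Section 3.1.07 belongs to the earlier study and is not split by class, and barrier modelling is mentioned only as a possible use.

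The strongest objection is to a simple exclusion rule. Step 6 of the working shows that it can reverse the bias. That stands, and it determines the form of the fix.

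**Conclusion.** The gap is real and should be closed. The supplied text defines the possibly related class only by a broad code set and gives no rule for a co-coded alternative cause. As written, disease-driven readmissions can be counted in the burden. On the assumptions shown, with equal disease in both routes, the inflation is 0.7 to 5.4 percentage points. At the middle setting (t = 20%, r = 15%) it is 2.4 points, or 0.024 × 45,000 = 1,080 to 0.024 × 75,000 = 1,800 patients.

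Distortion of the route comparison is possible but conditional on unequal disease within an anatomical group. Under the unequal shares assumed here, the spurious open-to-laparoscopic ratio lies between 1.02 and 1.64. Every one of these sizes rests on assumed inputs. They show that the issue can matter, not how large it is in this cohort.

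**What to change.** In Section 3.1.08:

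1. Keep the broad possibly related class, for comparability with the earlier studies. Split it with a pre-specified code list into readmissions with an alternative cause co-coded (for example malignancy, obstructed hernia, inflammatory bowel disease) and readmissions with none. State which diagnosis positions on the record count.
2. Report the burden, and the route comparison within each anatomical group, both with and without the co-coded readmissions, as upper and lower versions. Neither replaces the other.
3. Stratify or adjust the route comparison by index malignancy, taken from the index ICD-10 codes.
4. Report the directly related class separately. Leave the third class as its own outcome outside this split.

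The cost is plan wording, one further code list and a second set of tables; all the codes needed are already requested. Section 3.3.01 refers to journal queries on presented data. If the analysis has already been run, the list should be fixed before the split is tabulated by route, and the result labelled as added later.

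The downside is that some true adhesive episodes carry a co-coded disease, possibly more often in one route. The narrower version can then be too low, or biased in the opposite direction. It also keeps any disease-driven readmission whose cause was not coded. The two versions show how sensitive the results are to this rule; they are not strict limits on the true value.

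### An adhesion code is the only stated condition for the direct class, with no precedence over the third class, so a planned second-stage operation with incidental coded adhesiolysis can count as a direct adhesion readmission

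*Combined protocol and SAP*

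**What the plan says.** Section 3.1.08 names three outcome classes for readmissions: "directly related to adhesions, possibly related to adhesions, and readmission with surgery that might be complicated by adhesions". For the first of these the rule is: "For a readmission to be classified as directly related to adhesions, an explicit adhesion reference was required in the operative OPCS-4 or diagnostic ICD-10 coding". No other condition is given. Main and secondary code positions are not distinguished, nor are planned and unplanned admissions, and nothing says which class applies when a readmission meets two.

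Entry to the data set is equally broad: "Only readmissions coded by one or more relevant ICD-10 or OPCS-4 code need to be included". The statement "There are no further exclusion criteria" concerns patients, not readmissions. The variable table in 4.3 asks for ICD-10 and OPCS-4 codes, laparoscopic or open approach and continuous inpatient stay. It does not list elective or emergency admission type.

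Section 3.1.07 states the purpose: "Comparison of readmissions for adhesion- related complications after open and laparoscopic surgery will be made". For analysis, 3.1.08 divides index operations by anatomy into "hindgut, female reproductive tract, and foregut or other", each split by route. On covariates it says: "As baseline characteristics we will only require age and sex".

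**The concern.** The third class shows that the plan recognises two different situations: adhesions that cause an admission, and adhesions met during surgery done for another reason. The coding rule does not keep them apart. Take a patient who returns for planned closure of a stoma made at the index operation and has adhesions divided on the way in. If the adhesiolysis is coded, the admission satisfies the direct rule, and it also fits the description of the third class. The adhesions are real, but they did not bring the patient to hospital.

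Two results are at stake. One is the route comparison. If planned second-stage operations are more common after open than after laparoscopic index surgery, or the reverse, the direct rate partly measures how often a second operation was planned. Broad anatomical groups with age and sex as the only baseline data would not remove that difference. The other is the burden estimate. Admissions that would have happened without adhesions add to the direct count whatever their split by route.

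**Working it through.** **The plan's own figures.** The only derived figure is the incident population in 3.1.08: 70,000 − 25,000 = 45,000 and 100,000 − 25,000 = 75,000. Both reproduce. No rate is stated for the direct class. The 34.6% over 10 years in 3.1.07 combines direct and possible readmissions. There is therefore no figure of the plan's to correct, and what follows is an illustration.

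**Inputs, all assumed:**
- t, the rate of direct readmission truly caused by adhesions, equal on both routes (no true effect): 3% or 5%.
- s, the share of index patients who have a planned closure: 25% open and 12% laparoscopic, or, in a milder case, 20% and 15%.
- q, the share of closures carrying an adhesion code: 5%, 10% or 20%.

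**Formula.** Observed direct rate = t + s × q. For t = 3%, shares 25% and 12%, and q = 10%:
- Open: 3 + 25 × 0.10 = 5.5%.
- Laparoscopic: 3 + 12 × 0.10 = 4.2%.
- Laparoscopic/open ratio: 4.2 / 5.5 = 0.764.

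The cells below give observed open % / laparoscopic %, then the laparoscopic/open ratio.

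| s open/lap. | t | q = 5% | q = 10% | q = 20% |
|---|---|---|---|---|
| 25% / 12% | 3% | 4.25 / 3.60, 0.847 | 5.50 / 4.20, 0.764 | 8.00 / 5.40, 0.675 |
| 25% / 12% | 5% | 6.25 / 5.60, 0.896 | 7.50 / 6.20, 0.827 | 10.00 / 7.40, 0.740 |
| 20% / 15% | 3% | 4.00 / 3.75, 0.938 | 5.00 / 4.50, 0.900 | 7.00 / 6.00, 0.857 |
| 20% / 15% | 5% | 6.00 / 5.75, 0.958 | 7.00 / 6.50, 0.929 | 9.00 / 8.00, 0.889 |

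The ranges are 0.68 to 0.90 for the wider gap and 0.86 to 0.96 for the milder one.

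**Check on the formula.** Adding the two parts counts a patient twice if both events occur. At patient level the rate is 1 − (1 − t)(1 − s × q). The worked example becomes 1 − 0.97 × 0.975 = 5.43% and 1 − 0.97 × 0.988 = 4.16%, ratio 0.768. The choice of formula hardly matters.

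**Sensitivity to the inputs.** The patient-level formula was also run with t from 2% to 5%, shares of 10%/5%, 20%/10% and 20%/5%, and q from 5% to 20%. The open/laparoscopic ratio ran from 1.045 to 1.987, which is 0.96 down to 0.50 as laparoscopic/open. The table is therefore not a bound.

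**Equal shares.** With 5% on both routes the ratio is exactly 1.00. Planned closures still make up 4.5% (t = 5%, q = 5%) to 33% (t = 2%, q = 20%) of the counted direct events.

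**Reversed shares.** If the milder shares are exchanged (15% open, 20% laparoscopic), the ratio runs from 6.00 / 5.75 = 1.04 to 7.00 / 6.00 = 1.17. The direction follows entirely from which route is assumed to have more planned second stages.

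**The case against.** The strongest reply is that the text sets a necessary condition. An adhesion code is what the rule asks for as a minimum, and the plan never says that any code on any readmission is enough. A reader might infer that it does say so. That is the natural way to apply the rule, since nothing else is stated, but it remains an inference. The plan also has a third class in which planned reoperations could be placed, so the gap is a missing tie-break. This stands, and the point is limited to it.

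A reader might also infer that these events reflect the index operation and not adhesions. That goes too far. The index operation determines the opportunity to find and code adhesions, but a coded adhesiolysis still needs adhesions to be present.

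Stoma closure is an example chosen for this review and is not mentioned in the documents. Section 7 lists a code appendix and a protocol sent for IRB approval as separate attachments, and neither is in the text available. Any handling of closure codes there cannot be checked.

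The size is assumed throughout. The documents do not say which operations make up the hindgut group, and a broad mix could make the closure share much smaller than 25%. A reader might infer that the comparison is biased in favour of laparoscopy, but the documents do not support a direction. Nor do they say that the direct class alone feeds the cost modelling: 3.1.07 says only that the burden estimate can be used for it.

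The last objection concerns the remedy. A closure code identifies the procedure. It does not show that the admission was planned or that the adhesions were incidental. Taking every closure out of the headline class would misclassify closures driven by adhesive obstruction and reduce comparability in a study described as an update of SCAR. Section 3.3.01 also shows data access continuing for journal questions, so redefining the main class now could be post hoc. This is a good reason to add an analysis and leave the headline class alone.

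**Conclusion.** The point holds as a gap in the outcome definition. As 3.1.08 is written, nothing keeps a planned second-stage operation with an incidental adhesion code out of the direct class, and nothing settles whether the direct or the third class takes it.

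The open/laparoscopic comparison could be biased, but only if such operations, or the coding of adhesions at them, differ by route. With no true effect and the assumed inputs, the laparoscopic/open ratio lies between about 0.68 and 0.96. It is 1.00 if the shares are equal, and above 1 if the shares are reversed. The overstated burden does not depend on a difference between routes. It needs only that some planned second-stage operations carry an adhesion code. None of these sizes comes from the documents, and confidence in the practical importance is moderate. The change is worth making because it is cheap and would show whether the issue matters.

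**What to change.** In 3.1.08:

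1. Assign each readmission to exactly one of the three classes by a fixed, stated hierarchy.
2. Keep the direct class, defined by the adhesion code, as the version comparable with SCAR.
3. Add a pre-stated analysis in which readmissions with an OPCS-4 code for closure of a stoma or restoration of continuity go to the third class, whether or not an adhesion code is present. List the codes used.
4. Report the direct class and the open/laparoscopic comparison under both definitions, side by side. If the analysis is added after results are known, label it as such.

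The OPCS-4 codes for index operation and readmission are already requested in 3.1.08 and 4.3, so no new variable is needed. The cost is a small amount of extra analysis. In the added analysis a few closures driven by adhesive obstruction will leave the direct class. Reporting both versions shows how much the results depend on moving coded closures.

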 Quality (Clinical, Educational, etc)												
3.1.05	Does the proposal require the use of information which can identify or potentially identify individuals?	No										
3.1.06	Access is being requested to data from which sources? (tick as many as are relevant)											

- A single NHS Scotland Board (excluding NSS)
- NHS National Services Scotland
- More than one NHS Scotland Board
- A national NHS Scotland system/database
- More than one NHS Scotland system/database
- Community Health Index (CHI) database
- NHS Central Registry

If other, please give details:

**3.1.07** *Provide a full, clear concise outline of the proposal background – describe why it is needed, aims and objectives and envisaged benefits to the public and/or patients:*

Adhesion formation is the most common cause for long – term complications in abdominal surgery. Abdominal surgery is performed by a multitude of specialists, including general surgeons, gynaecologists, vascular surgeons and urologists. In Scotland, like many other developed countries, adhesion- related complications cause a huge burden of morbidity. Adhesion-related complications comprise various clinical entities such as small bowel obstruction, chronic pain and female infertility.

In 1999 [name] demonstrated in the SCAR studies, using data from the Scottish National Health Service record linkage database, that as many as 34.6% of patients undergoing abdominal surgery are readmitted for complications directly or possibly related to adhesion formation in 10 years after surgery.

Since this landmark study a number of strategies were introduced to reduce adhesion formation. First are the so-called 'anti-adhesion' barriers. Almost simultaneously there has been the rise of minimal invasive surgery. Minimal invasive surgery is associated with less extensive peritoneal injury and adhesion formation.

While minimal invasive surgery became adopted quickly, the use of anti-adhesion barriers remains marginal. Many surgeons therefore feel that with laparoscopy further adhesion prevention is not necessary, despite some evidence that incidence of adhesion- related complications is still considerable.

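### Persisting symptoms that prompted the index operation can be counted as possible adhesion readmissions, which inflates that class and could bias the route comparison in either direction

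*Combined protocol and SAP*

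**What the plan says.** All of this is in Section 3 of the application, under 3.1.07 and 3.1.08.

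- **Cohort.** All patients with initial abdominal or pelvic surgery from June 2009 to June 2011 are eligible. The one exclusion is earlier surgery: "We will exclude patient who had had abdominal or pelvic operation in the 5 years before 2009". The text then adds: "There are no further exclusion criteria".
- **Directly related class.** Here "an explicit adhesion reference was required in the operative OPCS-4 or diagnostic ICD-10 coding".
- **Possibly related class.** The plan notes that adhesions may go uncoded when a readmission involves no surgery. Its example is that "a conservative treated small bowel obstruction might only be coded as abdominal pain, nausea, and vomiting". It continues: "Therefore we will define a broader set of operative codes and diagnostic codes that might indicate a possibly adhesion- related complication".
- **Grouping.** Three anatomical groups are formed, each split into laparoscopic and open. Indication is not a grouping factor.
- **Baseline data.** "As baseline characteristics we will only require age and sex". Index diagnoses are nevertheless requested: "From the initial admission with abdominal or pelvic surgery we need ICD- 10 codes and OPCS- 4 codes". No use of them to identify the reason for operating is stated.
- **Complications named in the background.** These are "small bowel obstruction, chronic pain and female infertility".
- **Purpose.** The estimate is to describe the burden in Scotland, to serve as a model for other European countries, and to model the effect of wider use of anti-adhesion barriers on morbidity and cost.

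**The concern.** The cohort is incident for surgery but not for the symptoms that the possible class is meant to pick up. Someone whose index operation was done for abdominal pain already has the complaint at baseline. If the operation does not relieve it, the next admission coded for pain meets the purpose of the possible class, although adhesions from the index operation need play no part.

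Two results are at stake. The first is the possible-class burden, which would absorb failure of the index operation to cure the original complaint. An anti-adhesion barrier cannot prevent a complaint that came before the operation, so a model of preventable burden built on this figure would be too optimistic. The second is the route comparison, which would move if symptom-indicated operations were commoner on one route than the other. The plan already accepts the principle for prior surgery, which it excludes because adhesions present beforehand could affect the results. It does not extend that reasoning to a pre-existing outcome.

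**Working it through.** **The plan's own figure.** The expected incident population reproduces: 70,000 − 25,000 = 45,000 and 100,000 − 25,000 = 75,000. The text gives no event rate by class, no share of symptom-indicated operations and no readmission rate for persisting symptoms. Every risk below is therefore an assumption, unless stated otherwise.

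**Step 1. Does the text allow the miscount?** No stated exclusion, stratum, covariate, washout or code-matching rule separates a readmission for the index complaint from a new one. The possible class is introduced so that symptom-only admissions count. Followed as written, the miscount can occur.

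**Step 2. Burden, with no route imbalance.** Let R be the true risk, p the share operated on for a counted symptom and q their chance of readmission for the persisting symptom, acting independently of R. Observed risk = 1 − (1 − R)(1 − pq). With R = 10%:

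- p = 10%, q = 10%: 1 − 0.90 × 0.99 = 10.9%
- p = 20%, q = 30%: 1 − 0.90 × 0.94 = 15.4%

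Equal shares leave a null ratio at 1.00 but dilute a real effect. With true risks of 7% and 10% (ratio 0.70), the same two cases give 7.93/10.9 = 0.73 and 12.58/15.4 = 0.82.

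**Step 3. Route comparison, no true route effect.** Let b be the possible-class risk in other patients and r the risk in symptom-indicated patients. Risk on a route = p·r + (1 − p)·b, which equals b + p·(r − b). With b = 5% and r = 20%:

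- p = 15%: 0.15 × 0.20 + 0.85 × 0.05 = 0.0725
- p = 5%: 0.05 × 0.20 + 0.95 × 0.05 = 0.0575

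If the larger share is laparoscopic, the laparoscopic to open ratio is 0.0725/0.0575 = 1.26. If it is open, the ratio is 0.0575/0.0725 = 0.79. On the route with the larger share, 0.15 × 0.15/0.0725 = 31% of patients with a possible-class readmission are excess. On the other route it is 0.05 × 0.15/0.0575 = 13%.

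**Step 4. Dependence on base risk.** Here the excess r − b is held fixed (10, 15 or 20 points) while b changes. Each column heading gives the laparoscopic share, the open share and the excess.

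| b | 10%, 5%, 10 points | 15%, 5%, 15 points | 20%, 5%, 20 points | 5%, 15%, 15 points |
|---|---|---|---|---|
| 5% | 0.060/0.055 = 1.09 | 0.0725/0.0575 = 1.26 | 0.090/0.060 = 1.50 | 0.79 |
| 10% | 0.110/0.105 = 1.05 | 0.1225/0.1075 = 1.14 | 0.140/0.110 = 1.27 | 0.88 |
| 20% | 0.210/0.205 = 1.02 | 0.2225/0.2075 = 1.07 | 0.240/0.210 = 1.14 | 0.93 |

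The Step 2 model agrees. With shares of 20% laparoscopic and 10% open, R = 10% and q from 10% to 30%, the ratio runs from 11.8/10.9 = 1.08 to 15.4/12.7 = 1.21. With the shares reversed it runs from 0.92 to 0.82. The only risk in the documents is 34.6% (3.1.07), a 10-year figure for direct and possible readmissions combined. Used as R, it gives 1.02 to 1.05 for the first set of shares.

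**Step 5. Would a small bias be visible?** Take one third of 45,000 patients, split equally by route (7,500 each), with R = 10%, shares of 20% and 10%, and q = 20%. Observed risks are 13.6% and 11.8%, and the standard error of the difference is about 0.0054. The difference of 0.018 is about 3.3 standard errors, so p < 0.05 arises with probability 0.91. At q = 10% the probability is 0.41.

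**The case against.** The strongest case against has five parts.

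- **The lists are unseen.** The code appendix and the protocol sent for ethics approval are named in Section 7 but are not in the reviewed text. Pain, nausea and vomiting appear as an example, and the background names clinical complications rather than outcome codes. This stands: a reader might infer that abdominal pain is a listed outcome code, but the text shows only that the class is intended to catch such admissions. Likewise, the absence of a matching rule can be asserted only of this text.
- **Route bias is not shown.** A reader might infer a spurious laparoscopic excess, on the view that diagnostic operations are mostly laparoscopic, and expect it to be worst in the female reproductive tract group. The documents give no indication mix by route or by anatomical group, and reversed shares turn the ratio below 1. Neither inference is supported.
- **The larger ratios come from a low base risk.** This stands, as Step 4 shows. The 34.6% figure is not a direct substitute, because it covers a longer period and two classes together.
- **Much of the route problem is confounding by indication or procedure.** That is fair. Even so, adjusting the route contrast would leave the persisting symptoms in the burden figure.
- **Restricting the main analysis would cost comparability.** The study updates the SCAR studies and wants a national figure for all first operations, and it treats chronic pain as an adhesion complication. This stands, and it argues for reporting both estimates rather than replacing one with the other.

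None of this removes the gap: nothing in the text separates a persisting complaint from a new one.

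**Conclusion.** The concern holds for the possibly related class. As written, the plan can score the complaint that led to the index operation as a possible adhesion readmission, so that burden is inflated whenever such patients exist and their symptom codes count. In the illustration with equal shares, a true 10% is observed as 10.9% to 15.4%.

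The effect on the route comparison is conditional. It needs unequal symptom-indicated shares, or a real route effect to dilute, and the documents show neither. Under the assumed inputs the null ratio is 1.26 or 0.79 depending only on which route has the larger share, and it approaches 1 as base risk rises. Direction and size are unknown. With a cohort this large, even a modest bias could reach nominal significance.

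The directly related class requires an explicit adhesion code and is essentially unaffected. The conclusion assumes that the unseen code list includes symptom codes, as the plan's own rationale indicates.

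**What to change.** In 3.1.08:

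1. Keep the full-cohort estimate, so that results stay comparable with the SCAR studies.
2. From the index ICD-10 codes already requested, flag index admissions whose diagnosis is itself a symptom code on the possible list. Limiting the flag to symptom codes avoids sweeping in index operations for conditions such as obstruction.
3. Pre-specify that the possible-class burden and the route comparison are reported with and without the flagged stratum, removing it from numerator and denominator alike. Show the stratum separately, by route.
4. When modelling the burden that barriers could prevent, use the estimate without the stratum as the sensitivity bound.
5. Leave the directly related class unchanged.

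The cost is one flag and one extra table, with no new data. Two limits should be stated. Some true adhesion pain is set aside in the restricted analysis. Patients operated on for pain but coded with the condition found escape the flag. The restricted estimate is therefore a sensitivity value, not a strict lower limit.
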